#### **6.1.4. Subject Identification**

All subjects will be assigned a subject identification number to identify the subject on all study-related documents in order to maintain subject anonymity. Subject ID will be assigned at the time of enrollment.

## **6.2. Subject Inclusion Criteria**

Subjects must meet all of the following characteristics for inclusion in the study.

- Male or female, aged 35 to 75 years at the time of surgery.
- Willing and able to give voluntary informed consent to participate in this investigation.
- Full thickness tear of the rotator cuff
- Tear requires repair within one year of initial diagnosis.
- Tear must be anatomically repairable (must be able to get tendon back to the medial position on the footprint and at least back to the tuberosity).

- Willing and able, in the opinion of the Investigator, to cooperate with study procedures, and willing to return to study site for all required post-operative study visits.

### 6.3. Subject Exclusion Criteria

Subjects with any of the following characteristics must be excluded from participation in the study.

- Evidence of acute trauma including fracture or dislocation of the shoulder joint.
- Chronic retraction.
- Evidence of active infection, osteomyelitis, sepsis or distant infection, which could spread to the index joint.
- Subject has had previous rotator cuff, arthroplasty or fracture procedures on the operative shoulder.
- Subject has had acromioplasty or diagnostic arthroscopy on the operative shoulder within one (1) year prior to scheduled surgery date.
- Evidence of osteomalacia or other metabolic bone disorder(s), which may impair bone or soft tissue function.
- Evidence of other significant shoulder pathology including (Type II-IV lesion, Bankart lesion, Hill Sachs lesion).
- Patient has grade 4 changes to articular cartilage in operative shoulder
- Inflammatory arthropathies.
- Significant muscle paralysis of the shoulder girdle.
- Painful pathologies of the cervical spine.
- Comminuted bone surface, which would compromise secure anchor fixation.
- Non-surgical rotator cuff associated treatment, such as corticosteroid injection, within one (1) month prior to scheduled surgery date.
- Participating in another investigational trial or ongoing study that would interfere with the assessment of the primary and secondary outcomes.
- Female patient who is pregnant, nursing, or of childbearing potential while not practicing effective contraceptive methods.
- Major psychiatric illness, developmental handicap or inability to read and understand the English language.
- Major medical illness that would preclude undergoing surgery.
- Known to be involved in any active injury litigation claims relating to the study shoulder.
- Unwilling or unable to be assessed according to study protocol for two years following surgery.
- Patient requires a concomitant SLAP repair procedure in operative shoulder.
- Surgeon plans to use a Platelet Rich Plasma product or another therapy intended to augment healing of the rotator cuff in the study procedure.
- Protocol specified surgical technique cannot be followed for this subject.
- Rotator cuff repair will be done via open (as opposed to arthroscopic) procedure.

- Any other reason (in the judgment of the investigator).

#### **6.4. Withdrawal of Subjects from Study**

All reasonable efforts should be made to retain the subjects for the duration of this study. Once a subject has been withdrawn from the study (pre-maturely or at completion of the study), the study termination form should be completed.

##### **6.4.1. Voluntary Withdrawal by Subject**

Study participation is voluntary and subjects may withdraw at any point during the study. If a subject withdraws from the study, the investigator will make all reasonable efforts to determine the reason for the subject's withdrawal and will document the reason on the applicable form. After a subject withdraws from the study, no effort will be made to replace or follow the subject.

##### **6.4.2. Withdrawal by Investigator**

The investigator may withdraw subjects from the study for many reasons, including but not limited to the following:

- Occurrence of a serious adverse event
- Investigator's discretion to withdraw subject for safety reasons
- Subject noncompliance with visits and/or assessments
- Subject is lost to follow-up (as defined per section 6.4.3)

##### **6.4.3. Lost to Follow-Up**

Subjects will be defined as lost to follow-up when the following procedures have been documented in the subject's source documentation and End of Study CRF:

- At least 2 phone calls made on separate dates to the subject are not returned
- A certified letter is sent to the subject's last known address and the subject does not reply after 30 days

##### **6.4.4. Documentation of Study Completion Status**

The completion status of the subject (e.g. completed per protocol, subject withdrawal, device removed, death, lost-to-follow-up, or other reason) should be recorded and the reason for withdrawal, if applicable, should be documented in the source documentation.

### **7. Informed Consent**

Investigators are responsible for obtaining and documenting the voluntary informed consent of the study subjects prior to conducting any study-related assessments per 21 CFR Part 50. The informed consent form should include all elements noted in 21 CFR Part 50 Subpart B and Good Clinical Practice (GCP) guidelines.

In obtaining informed consent investigators must adhere to 21 CFR Part 50 and GCP guidelines and to the ethical principles that have their origin in the Declaration of Helsinki. Prior to beginning the trial the investigator must obtain written and dated approval of the informed consent form. Subjects will receive a copy of the initial signed and dated informed consent form prior to the subjects' participation in the trial and any revised informed consent forms during the duration of the trial.

**The subject must sign and date the consent form in the presence of the investigator or the investigator's designee, who must sign and date the consent form in the presence of the subject.**

The informed consent form and any other written information provided to subjects should be revised whenever important new information becomes available that may be relevant to the subject's continued consent. All revised informed consent forms must have written and dated IRB approval in advance of use.

The communications with the subject regarding informed consent process (initial and subsequent) should be documented in the medical record.

## **8. Study Procedures**

### **8.1. Prior to Study Initiation**

The investigator must ensure the activities below are completed prior to initiating the study.

#### **8.1.1. IRB Approval**

The protocol and informed consent materials must be approved by the IRB prior to patient enrollment.

#### **8.1.2. Documentation of Qualifications**

A current, signed, dated CV and a current medical license for the principal investigator and sub-investigators must be available prior to the study start.

#### **8.1.3. Sponsor Site Initiation**

A site initiation meeting with the sponsor and the site must be completed prior to initiating study activities and the site must have written approval from the sponsor to initiate the study.

## **8.2. Study Assessments**

### **8.2.1. Visit 1- Baseline Assessment**

The following information will be collected prior to the study procedure:

- Informed Consent
- Medical History & Demographics: Record general subject medical history and demographics.
- Patient Outcomes: Subject to complete VAS, WORC, SANE and PENN scales
- Range of Motion Assessment

### **8.2.2. Visit 2- Procedure**

The following information will be collected at this visit:

- Surgical Information
- Device Details: Be sure to keep stickers from the device packaging and record device details in the patient medical record and the Operative source documentation form.
- Adverse Events: Record any adverse events experienced by the patient

### **8.2.3. Follow-Up Visits (6WK, 6M, 12M, 24M)**

The following information will be collected at each follow-up visit:

- Patient Outcomes: Subject to complete VAS, WORC, SANE and PENN scales
- Range of Motion Assessment (6WK, 6M+, 24M)
- Patient Satisfaction
- US at  $\geq$  6M only
- MRI at 6 WK only
- CT Scan at 24M only

#### 8.2.4. Rehabilitation Protocol

Each patient will be given a standardized rehabilitation protocol, which should be followed.

#### 8.2.5. Radiological Procedures

All enrolled patients will receive one CT scan over the course of their study participation. All CT Scans will be conducted utilizing the CT Protocol. Data will be captured on the CT Evaluation Form.

#### 8.2.6. Additional Visits

Additional visits will not be recorded, unless they are due to an adverse event. In this case, an Adverse Event form should be completed.

Table 1: Schedule of Events

	BL	Proc	6WK	6M	12M	24M
Informed Consent	✓	-	-	-	-	-
Inclusion/Exclusion	✓	-	-	-	-	-
Demographics/Medical History	✓	-	-	-	-	-
Surgical Details	-	✓	-	-	-	-
Physical Exam-ROM	✓	-	✓	✓ 1	-	✓
Visual Analogue Scale (VAS)	✓	-	✓	✓	✓	✓
PENN	✓	-	✓	✓	✓	✓
WORC	✓	-	✓	✓	✓	✓
SANE	✓	-	✓	✓	✓	✓
EQ-5D	✓	-	✓	✓	✓	✓
Ultrasound	-	-	-	✓ 1	-	-
MRI	-	-	✓	-	-	-
CT Scan	-	-	-	-	-	✓
Patient Satisfaction	-	-	✓	✓	✓	✓
Adverse Event Assessment	-	✓	✓	✓	✓	✓
End of Study/Exit	*	*	*	*	*	*

1Ultrasound will be done at  $\geq$  6 months post-procedure.

\* End of Study will be noted on study spreadsheet at any point throughout the trial.

## 9. Risk Analysis

### 9.1. Manner in Which Potential Risks Will Be Minimized

The investigators have proper experience and training to support the use of the current device. The investigators in this study have extensive experience in rotator cuff repair.

Careful attention to subject selection criteria and surgical techniques may reduce the potential of any adverse effects.

Potential risks associated with suture anchors are the following:

- Mild inflammatory reaction
- Foreign body reaction
- Infection, both deep and superficial
- Allergic reaction

### 9.2. Potential Benefits

Participation in this study may offer no benefit to subjects. However, it is possible that the use of HEALICOIL™ REGENESORB suture anchors could lead to improved tendon to bone repair.

## 10. Adverse Events

### 10.1. Definitions

An adverse event is defined as any untoward medical occurrence in a clinical investigation in which a subject is administered a study device and which does not necessarily have a causal relationship with the device. An adverse event can therefore be any unfavorable and unintended sign (including an abnormal laboratory finding or an abnormal radiographic finding), symptom, or disease temporally associated with the use of study device, whether or not related to the study device. The following are specific definitions of adverse events:

Adverse Event (AE) — any untoward medical occurrence in a subject, regardless if there is a relationship between the AE and the device.

Serious Adverse Event (SAE) — an adverse event that:

- leads to a death
- leads to a serious deterioration in the health of a subject that results in a life-threatening illness or injury
- results in a permanent impairment of a body structure or a body function
- requires in-subject hospitalization or prolongation of existing hospitalization
- results in medical or surgical intervention to prevent permanent impairment to body structure or a body function
- results in congenital anomaly/birth defect

Adverse Device Effect (ADE) — any untoward and unintended response to a medical device (This definition includes any event that is a result of a user error).

**Unanticipated Adverse Device Effect (UADE)** — An UADE is defined as any serious adverse effect on health or safety or any life-threatening problem or death caused by or associated with this device that was not previously identified in nature, severity, or degree of incidence in the application of the device.

Device related adverse events can include any of the following:

- Any device implant component failure (e.g. breakage)
- Any device component experiencing dislocation, subluxation, subsidence, or migration.
- Unintended bone fractures.
- Nerve damage (as evidenced intra-operative or immediate postoperative by motor and/or sensory deficit not present preoperatively).
- Other adverse events as listed in the Risk Analysis section (9.0) that are deemed device related and serious.

## **10.2. Treatment for Adverse Events**

In the event of an adverse event, the investigator and/or other professional personnel in attendance will provide whatever appropriate medical treatment is indicated for the problem.

## **10.3. Documentation of Adverse Events**

All adverse events will be documented in the source documentation. Beginning after the study procedure has taken place, all AE's, including those measured, observed or volunteered, will be recorded on the applicable case report form. The investigator will review all documentation (e.g., hospital progress notes, laboratory, or diagnostic reports) relative to the event being reported. The investigator will then record all relevant information regarding an AE onto the study CRF.

The investigator will attempt to establish a diagnosis of the event based on signs, symptoms, and/or other clinical information. In such cases, the diagnosis should be documented as the AE and not the individual signs and symptoms.

When reporting an AE, the investigator will evaluate the event for duration, intensity, relationship and outcome.

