### Schedule of Events

	BL	Proc	6WK	6M	12M	24M
Informed Consent	✓	-	-	-	-	-
Inclusion/Exclusion	✓	-	-	-	-	-
Demographics/Medical History	✓	-	-	-	-	-
Surgical Details	-	✓	-	-	-	-
Physical Exam-ROM	✓	-	✓	✓ 1	-	✓
Visual Analogue Scale (VAS)	✓	-	✓	✓	✓	✓
PENN	✓	-	✓	✓	✓	✓
WORC	✓	-	✓	✓	✓	✓
SANE	✓	-	✓	✓	✓	✓
EQ-5D	✓	-	✓	✓	✓	✓
Ultrasound	-	-	-	✓ 2	-	-
MRI	-	-	✓	-	-	-
CT Scan	-	-	-	-	-	✓
Patient Satisfaction	-	-	✓	✓	✓	✓

Adverse Event Assessment	-	√	√	√	√	√
End of Study/Exit	*	*	*	*	*	*

Physical Exam at 6M will occur at the same visit as the 6+ month ultrasound.

Ultrasound will be done at  $\geq$  6 months post-procedure.

\* End of Study will be noted on study spreadsheet at any point throughout the trial.

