### Examples of an AE:

- Exacerbation of a chronic or intermittent pre-existing condition including either an increase in frequency or intensity of the condition.
- Significant or unexpected worsening or exacerbation of the condition/indication under study.
- A new condition detected or diagnosed after study device administration even though it may have been present prior to the start of the study.
- Pre- or post-procedure events that occur as a result of protocol-mandated procedures (e.g., invasive protocol-defined procedures, modification of a subject's previous treatment regimen).

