#### 10.4.

#### **Follow-Up of Adverse Events**

After the initial AE report, the investigator is required to proactively follow each subject until the event resolves. All AEs documented at a previous visit that are designated as ongoing will be reviewed at subsequent visits/contacts.

Adverse events will be followed until resolution, until no further changes in the event are expected (i.e. the point at which a subject experiencing a critical adverse event is treated successfully and stabilized even though he/she may continue to experience lingering sequelae that may never resolve), until the subject is lost to follow-up, or until it is agreed that further follow-up of the event is not warranted (e.g. non-serious, study therapy unrelated, mild or moderate adverse events ongoing at the subject's final study visit).

New or updated information shall be recorded by completing an AE follow-up CRF.

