### **11. Reporting of Adverse Events**

#### 11.1.

#### **Investigator Adverse Event Reports**

Investigators are responsible for reviewing all SAEs, ADEs, SADEs, and UADEs, determining the relationship to the device and documenting on the appropriate CRF. All SAEs, ADEs, SADEs and UADEs must be reported by the investigator to the IRB (as applicable) as soon as possible but no later than ten (10) working days after learning of the event. The investigator must submit a detailed report that will identify the description of symptoms, classification of the event, date of onset, severity, treatment, and outcome. Supporting medical records may be obtained as an adjunct to an adverse event report and placed in the subject's study file.

All AEs will be categorized as mild, moderate or severe based on the following definitions:

**Mild:** The subject is aware of the sign or symptom, but finds it easily tolerated. The event is of little concern to the subject and/or little clinical significance. The event is not expected to have any effect on the subject's overall health or wellbeing.

**Moderate:** The subject has discomfort enough to cause interference with or change in usual activities. The event is of some concern to the subject's health or wellbeing and may require medical intervention and/or close follow-up.

**Severe:** The adverse event interferes considerably with the subject's usual activities. The event is of definite concern to the subject and/or poses substantial risk to the subject's health or wellbeing. The event is likely to require medical intervention and/or close follow-up and may be incapacitating or life threatening. Hospitalization and treatment may be required.

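### Does Section 10.3 leave intra-operative adverse events off the case report form?

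*Combined protocol and SAP*

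**What the plan says.** Section 10.3 (Documentation of Adverse Events) contains three relevant statements. Every adverse event goes into the source documentation, with no start time given. CRF recording of all adverse events then starts at a stated point: "Beginning after the study procedure has taken place". The paragraph closes by having the investigator review the documentation and enter the relevant information on the study CRF, again with no start time.

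Section 8.2.2, which covers the Procedure visit, includes the item "Adverse Events: Record any adverse events experienced by the patient". The row "Adverse Event Assessment" is ticked at the Procedure visit and at 6WK, 6M, 12M and 24M, but not at baseline, both in the Schedule of Events after the Protocol Summary and in Table 1.

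Section 11.1 adds a separate duty for the more important events: "Investigators are responsible for reviewing all SAEs, ADEs, SADEs, and UADEs, determining the relationship to the device and documenting on the appropriate CRF". It sets no start time.

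Section 3.1.3 names the between-group difference in complication rates as a safety endpoint, and the Protocol Summary lists it among the secondary endpoints. The term complication is not defined, and no data source for the comparison is given.

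**The concern.** Section 10.3 appears to open the CRF only once surgery is over, while Section 8.2.2 and the Schedules expect adverse events to be picked up at surgery. Other text also suggests that events outside the post-operative period count. Section 10.1 includes nerve damage that shows itself during the operation among possible device-related events. The examples of an adverse event include "Pre- or post-procedure events that occur as a result of protocol-mandated procedures".

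The trial compares two implanted anchors, so what happens during insertion bears on safety. If the complication comparison is drawn from the adverse event CRF (an assumption, since no source is named), a site following 10.3 to the letter and a site following 8.2.2 could count different events. Some intra-operative events would then be missing from the comparison or recorded unevenly.

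**Working it through.** There is no plan figure to reproduce. The check is a comparison of the passages, followed by a look at whether the gap can be sized.

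**Step 1: which record does each passage govern?**

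| Place | Record named | Start time |
|---|---|---|
| 10.3, first sentence | Source documentation | None |
| 10.3, second sentence | CRF | After the procedure |
| 10.3, end of first paragraph | CRF | None |
| 8.2.2 | None for adverse events; the device-details item names an operative source form | Procedure visit |
| Both Schedules | None (an assessment is ticked) | Procedure visit |
| 11.1 | CRF, for SAEs, ADEs, SADEs and UADEs | None |

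Only the second sentence of 10.3 attaches a start time to the CRF. Section 8.2.2 and the Schedules say when events are to be looked for and recorded, but not on which form. A site that writes an intra-operative event into the source record on the day, and completes the CRF once the operation is finished, complies with every row of the table. The last sentence of that paragraph of 10.3, which has the investigator review the record and then transfer the information, favours this reading without settling it.

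**Step 2: what would be lost on the literal reading?** Take each kind of event that could arise before the end of surgery.

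- *Serious.* Goes to a CRF under 11.1.
- *Device effect, serious or not.* Goes to a CRF under 11.1. Section 10.1 counts user error as an adverse device effect, so mishaps in handling the anchor are included. So is intra-operative nerve damage when it is judged device-related.
- *Non-serious, not a device effect, noticed or still present after surgery.* The examples include "A new condition detected or diagnosed after study device administration". Section 10.4 adds "All AEs documented at a previous visit that are designated as ongoing will be reviewed at subsequent visits/contacts". Such an event is therefore met again after the start point in 10.3.
- *Non-serious, not a device effect, over by the end of surgery.* Required in source documentation but, read literally, not on the CRF.
- *Non-serious, before surgery, caused by a protocol-mandated procedure.* Also exposed, but almost nothing can fall here. Before surgery, Section 8.2.1 and the Schedules list consent, eligibility, history and demographics, questionnaires and range of motion. MRI, ultrasound and CT all come after surgery. Section 10.1 also ties an adverse event to a subject who has been administered a study device.

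The fourth class is in effect the whole of the gap.

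**Step 3: can the gap be sized?** The documents give no rate of intra-operative events, so the number affected cannot be computed. If all 68 subjects are randomized 1:1, each arm has 68/2 = 34, and one subject whose only event went unrecorded would shift that arm's rate by 1/34 = 2.9 percentage points. Enrollment is at consent (6.1.2), before randomization (6.1.3), so fewer may be randomized. With an illustrative 60, the figure is 1/30 = 3.3 points. These figures are the weight of one subject in an arm and do not measure the defect. With equal arms, the difference between groups moves only if the arms lose unequal numbers of such subjects, and nothing in the wording treats the arms differently.

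**The case for a change.** The best case for a change is that the mismatch is plain and the repair is one sentence. Of the visit lists in Section 8.2, only the one for the Procedure visit names adverse events, so the authors evidently wanted events captured there. Section 6.1.3.1 blinds the subjects and the radiologists reading MRI and CT, but not the investigator who records events and judges their relation to the device. An unclear start time leaves discretion with someone who may know the arm, and discretion is one way in which the arms could lose unequal numbers. Source records alone do not put an event into a comparison based on the CRF.

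Part of this stands. The start clause in 10.3 is loosely worded, and the possible reading that it concerns only when the form is completed is not confirmed anywhere. The discretion argument is sound in principle, but on the start-time question it reaches only the fourth class in Step 2. Insertion events that involve the anchor are device effects and go to a CRF under 11.1 whatever 10.3 means. The documents offer no sign that the fourth class would be uneven between arms, and its members can be recovered from source.

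Going further would create new difficulties. Extending CRF recording to pre-procedure events would not match the Schedules, which have no adverse event tick at baseline. Entering such events at the Procedure visit would fail for a subject who consents and withdraws before surgery. Naming the adverse event CRF in Section 3.1.3 as the source for complications would set a counting rule for an undefined term. Since 3.1.3 lists adverse events and complication rates separately, it would also risk merging the two. That would be a new design decision and would not reconcile the existing text.

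**Conclusion.** No change follows. The start clause in Section 10.3 sits awkwardly beside Section 8.2.2 and the Procedure ticks, but the passages can all be followed together. On the strictest reading, the exposure is confined to non-serious, non-device events that begin and end during surgery, plus a pre-procedure class that is nearly empty. The size cannot be quantified from the documents, and no gain from a change has been shown. Following the plan as written leaves the safety comparison sound, and the primary endpoint and sample size are not involved.

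This rests on three points: Section 11.1 operates as written, with no start time; 10.3's requirement for all events in source documentation is met; and any effect on complication rates depends on the unstated assumption that the adverse event CRF is their source. Aligning the start time in 10.3 with 8.2.2 would be harmless tidying if the protocol were opened for another reason, but no conclusion of the trial depends on it.
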